4. PARTICIPANT SELECTION

4.1 Inclusion Criteria

- 4.1.1 Participants must be at high risk as defined by a history of breast cancer (invasive or DCIS) and be at least 5 years out from diagnosis, or lobular carcinoma in situ (LCIS), or proliferative benign breast disease such atypical ductal hyperplasia (ADH), atypical lobular hyperplasia(ALH) or genetic test confirmation of BRCA 1/2 mutation carrier or have a breast cancer risk assessment $\geq 1.7\%$ in 5 years or a lifetime risk $\geq 20\%$.
- 4.1.2 No evidence of disease (in situ or invasive cancer that would normally be treated by resection) at trial entry as determined by the investigator. Diagnosis of invasive cancer must be at least 5 years prior to initiation on trial.
- 4.1.3 Female ≥ 18 years as breast cancer is extremely rare in women less than 18 years.
- 4.1.4 ECOG performance status ≤ 1 (Karnofsky $\geq 70\%$; see Appendix A)
- 4.1.5 Participants must have normal organ and marrow function as defined below:
 - Leukocytes $\geq 3,000$ /microliter
 - Absolute neutrophil count $\geq 1,500$ /microliter
 - Platelets $\geq 100,000$ /microliter
 - Total bilirubin within normal institutional limits
 - AST (SGOT)/ALT (SGPT) $\leq 1.5 \times$ institutional upper limit of normal (ULN)
 - Creatinine $\leq 1.5x$ institutional ULN

Hemoglobin	≥10 g/dL
TSH	within normal institutional limits
Triglycerides	≤300 mg/dl
Total Cholesterol	≤300 mg/dl

- 4.1.6 ≥ 6 months from all previous breast cancer treatment (including endocrine therapy).
- 4.1.7 Participants must have adequate accessible breast tissue as determined by the treating physician, consisting of one breast unaffected by invasive cancer, which has not been radiated. A history of benign core biopsy of this breast will be permitted.
- 4.1.8 Participants need to have had any breast imaging with a normal/benign (bi-rads 1 or 2) result within 180 days of Day 0 and no further routine breast imaging planned during the course of the study (4 weeks). Exception: if the mammogram result was a bi-rads 0 and the imaging work-up (ultrasound and/or MRI) result comes back normal/benign (bi-rads 1 or 2) before treatment initiation, then participant is eligible.
- 4.1.9 For women of childbearing potential; negative pregnancy testing within 72 hours prior to or on study visit #1 (Day 0) and willingness to use adequate contraception during the study intervention. OR Post-menopausal defined as any one of the following 1) prior hysterectomy, 2) absence of menstrual period for 1 year in the absence of prior chemotherapy or 3) absence of menstrual period for 2 years in women with a prior history of chemotherapy exposure who were pre-menopausal prior to chemotherapy. In women of childbearing potential, effective contraception must be used for one month prior to the initiation of therapy, during therapy, and for at least one month following discontinuation of therapy. It is recommended that two reliable forms of contraception be used simultaneously. If participants are interested in enrolling and have not met the requirement for contraception, they will be seen in the clinic in 1 month for re-evaluation once they have met this requirement and ensure all other eligibility criteria is met prior to dose assignment.
- 4.1.10 Willingness to comply with all study interventions and follow-up procedures including the ability to apply the study drug to the breast.
- 4.1.11 Ability to understand and the willingness to sign a written informed consent document.
- 4.1.12 Ability to avoid exposure of the treated breast area to sunlight and artificial ultraviolet light during the use of bexarotene gel.

4.2 Exclusion Criteria

- 4.2.1 History of allergic reactions attributed to compounds of similar chemical or biologic composition to bexarotene gel, oral or topical retinoids.
- 4.2.2 Uncontrolled intercurrent illness including, but not limited to, ongoing or active infection, symptomatic congestive heart failure, unstable angina pectoris, cardiac arrhythmia, thromboembolic disease, or psychiatric illness/social situations that would limit compliance with study requirements.
- 4.2.3 Pregnant, or had given birth, or nursed at any time during the last 12 months.
- 4.2.4 Women with a history of any cancer within the last 3 years, except for non-melanoma skin cancer. See 4.1.1 as history of breast cancer must be at least >5 years from diagnosis.

- 4.2.5 Prior bilateral breast surgery (mastectomy, segmental mastectomy, or breast augmentation surgery including breast implants or breast reductions) or combination of breast radiation and surgery involving both breasts.
- 4.2.6 Prior history or evidence of metastatic breast cancer
- 4.2.7 Prior history of histologically confirmed bilateral invasive breast cancer.
- 4.2.8 Current use or <6 months since use of SERMS or Aromatase inhibitors or any other investigational treatment for breast cancer prevention or therapy.
- 4.2.9 Skin lesions that disrupt the stratum corneum (eg. eczema, ulceration) or any breakdown of the skin.
- 4.2.10 Current use of a retinol containing agent or any retinoid analogue drug within the last 30 days.
- 4.2.11 Dietary Vitamin A intake $\geq 5,000$ IU/day (as determined by dietary supplementation)
- 4.2.12 Treatment with any investigational drug or investigational biologic within 30 days of initiating study treatment or during the study.
- 4.2.13 History of HIV or active hepatitis C.

4.3 Inclusion of Women and Minorities

Women of all races and ethnic groups are eligible for this trial.

4.4 Recruitment and Retention Plan

Participants will be recruited for enrollment on this trial from the cancer prevention center, with particular attention to enhancing racial, ethnic and socioeconomic diversity. Prior to enrollment, the study will be discussed in detail with the participant, and possible toxicities will be presented. The informed consent document will be reviewed with the participant by the study physician or other medical staff authorized by the participating institution to obtain Informed Consent. Please refer to the study-specific Recruitment and Retention Plan for more details.

5. AGENT ADMINISTRATION

Intervention will be administered on an outpatient basis. Reported AEs and potential risks are described in Section 6.2.

5.1 Dose Regimen and Dose Groups/Gel Application

Participants will self-administer the bexarotene gel. Gel will be applied to one unaffected breast after freshly washed, either by washcloth, shower, or bath, preferably in the morning, (in order to minimize potential transfer to the partner at night). If morning shower is not possible, the subject will wash the one unaffected breast with a washcloth before gel application, to remove the prior day's dose. If a morning swim is planned, application

should be after the swim. No washing or immersion in water should occur for at least 4 hours following gel application. The gel should not be used near fire, flame or while smoking since it is flammable due to alcohol. Once dry, the gel is no longer flammable. Detailed instructions regarding application are in Appendix B and a demonstration of gel application will occur during the Baseline/Dose Assignment visit. The treated breast should be covered at all times to avoid transfer to other people and protect from natural or artificial sunlight; contact is permitted after the treated area has been washed with soap and water and washing is allowable after a minimum of 4 hours post-application.

Each bexarotene gel canister will contain 33 mL gel product and will be metered to dispense 10 mg of 1% bexarotene gel per pump. Cohorts 1 and 2 will receive 1 bexarotene gel canister containing 30 reliable doses. Cohort 3 will receive 2 bexarotene gel canisters containing 30 reliable doses each for a total of 60 reliable doses. The expansion cohort will receive either 1 or 2 bexarotene gel canisters depending on the maximum tolerated dose (MTD) as determined during the dose escalation group phase to assess bexarotene concentration in the breast tissue.

5.2 Gel Administration/Run-in Procedures

Each Bexarotene gel canister will contain 30 reliable doses of product metered to dispense 1mL per actuation, 1g of bexarotene gel per actuation. One gram of bexarotene gel contains 10mg of active bexarotene.

Participants in all dose levels will be instructed to apply the gel at 10mg (1 mL) every other day to one unaffected breast for the first 7 days of treatment. After the Day 8 phone call and confirmation that toxicity is at an acceptable range, participants assigned to 10mg/breast/daily will increase applications to daily. Participants assigned to 10mg/breast/every other day will continue to apply gel every other day. Participants assigned to 20mg/breast/daily will increase from 10mg (1mL) every other day to daily application for another 7 days. After the Day 15 visit and confirmation of acceptable toxicity, participants will increase to 20mg (2 mL) to the one unaffected breast daily for the remaining 2 weeks. All participants will continue to apply the gel to one unaffected breast as directed for a duration of 4 weeks. Participants in the dose expansion group will apply the gel with the same ramp up schedule as those in the dose escalation group for that dose level.

Participants will also receive moisturizing lotion [CeraVe] that can be applied to the breast to reduce and prevent redness that can be related from the study drug. CeraVe will be provided to all participants and they will be instructed to apply to the treated breast in the evening or at least 4 hours after application of study drug so it will not interfere with the absorption of study drug.

5.3 Contraindications

Participants are to avoid exposure of the treated breast skin to natural or artificial sunlight. This includes sunbathing or the use of tanning beds with the breasts exposed. Also, women who have dermatologic conditions causing the breakdown of skin should not use bexarotene gel.

5.4 Concomitant Medications

Women who are receiving endocrine therapy for breast cancer treatment or chemoprevention including tamoxifen, letrozole, anastrozole, fulvestrant, or exemestane at the time of screening will not be eligible. Participants may not have a history of allergic reactions attributed to compounds of similar chemical or biologic composition to bexarotene or retinoids. Participants must limit vitamin A intake to <5,000 IU/day. Participants should not concurrently use products that contain DEET (N,N-diethyl-m-toluamide), a common component of

insect repellent products. Otherwise, there are no restrictions on other medications, herbs, and vitamin and mineral supplements (other than study agents) while participating in the study.

All medications (prescription and over-the-counter), vitamin and mineral supplements, and/or herbs taken by the participant will be documented on the concomitant medication CRF and will include: 1) start and stop date, dose and route of administration, and indication. Medications taken for a procedure (*e.g.*, biopsy) should also be included.

5.5 Dose Modification

For any grade 1 adverse events or grade 2 adverse events that are not hypertriglyceridemia or skin related, no dose modifications will be made. For any grade 2 skin toxicity possibly, probably, or definitely related to study drug that persists for 3 days, drug will be held for 3 days. Participants at the lowest dose level will restart gel application at every 3 days dosing for 3 days (1 dose) and then increase back to every other day dosing. If grade 2 skin toxicity recurs and persists for 3 days, drug application will be discontinued and will be classified as a DLT. Participants in the second dose level (10mg daily) will hold for 3 days if toxicity is noted and resume at 10mg every other day for 4 days (2 doses) and then increase back to daily dosing. Participants at the highest dose level (20mg daily) will hold for 3 days and resume at 10mg daily for 3 days (3 doses) and then increase back to 20mg daily. Participants experiencing Grade 3 or Grade 4 toxicities of any attribution will be taken off study drug. Please see Table 1 for dose modification algorithm.

Table 1: Dose Modification Algorithm for Grade 2 Skin Adverse Events related to Bexarotene Gel

Dose Level	If Grade 2 Skin AE Persists for 3 Days	Dose Modification (If Skin AE resolves to \leq Grade 1)	If Grade 2 Skin AE Recurs and Persists for 3 Days
10mg/breast/every other day	Hold Study Drug for 3 days	Restart drug application at 10mg/breast/every three days for 3 days (1 dose) and then increase to original dose	Stop Drug
10mg/breast/daily	Hold Study Drug for 3 days	Restart drug application at 10mg/breast/every other day for 4 days (2 doses) and then increase to original dose	Stop Drug
20mg/breast/daily	Hold Study Drug for 3 days	Restart drug at 10mg/breast/ daily for 3 days (3 doses) and then increase to original dose	Stop Drug

Hypertriglyceridemia is a known systemic side effect with oral bexarotene formulation and will be monitored throughout the study. If grade 1 hypertriglyceridemia is noted, lipid profile will be continued to monitor weekly and at Day 22 blood specimen will be added for monitoring. If grade 2 hypertriglyceridemia is noted, drug will be held for 1 week and triglycerides will be rechecked. If normal, drug application will be resumed at the 1 dose level below. If triglycerides continue to be elevated or increase again, drug will be discontinued. If grade 3 hypertriglyceridemia is noted, drug will be discontinued and participant will be initiated on a statin. Triglycerides will be checked weekly until resolution and if elevation persists after 30 days, participant will be referred to their primary care physician for further management.

[figure not shown]

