Agent(s)/Supplier: Targretin® (bexarotene) gel 1% / Valeant Pharmaceuticals

NCI Contract # HHSN261201200034I

Protocol Version Date: 4/27/2021

**Protocol Revision or
Amendment #** Version 14

SCHEMA

A Phase I Dose Escalation Study of Topical Bexarotene in Women at High Risk for Breast Cancer

Part 1: Dose Escalation Group

Screening/Baseline Clinic Visit Day -30 to 0

Women with ADH, ALH, LCIS, Breast cancer survivors (DCIS or invasive) ≥ 5 years from their diagnosis, BRCA 1/2 mutation carriers, or elevated risk for breast cancer $\geq 1.7\%$ in 5 years or lifetime risk $\geq 20\%$

Intervention (N=30) Dose Assignment by a 3+3 dose escalation with 3 dose levels (Day 0):

Bexarotene 1% gel 10mg/breast/every other day or Bexarotene 1% gel 10mg/breast/daily or Bexarotene 1% gel 20mg/breast/daily for treatment duration of 4 weeks

Start Treatment (Day 1)

Phone Call (Day 8)

Assess AEs and review Gel Diary

Study Visits (Day 15 and Day 28 (End of Study))

Assess for AEs & review gel diary. Labs to assess safety (CBC, LFTs, Lipid Profile, Thyroid Function Tests, Calcium) on Day 15 and 28 visits. Serum bexarotene collected on Day 0 and Day 28 visit. Optional breast biopsy at Day 28 visit.

Follow Up Call (30 days \pm 7 days after Day 28)

Assess for any further AE and document resolution of any acquired AE during treatment

Primary Endpoint: Safety and Toxicity

Secondary Endpoints: Serum and Tissue Bexarotene level, calcium, lipid and thyroid function biomarkers

Part 2: Dose Expansion Group

Screening/Baseline Clinic Visit Day -30 to 0

Women with ADH, ALH, LCIS, Breast cancer survivors (DCIS or invasive) that are ≥ 5 years from their diagnosis, BRCA 1/2 mutation carriers, or elevated risk for breast cancer $\geq 1.7\%$ in 5 years or lifetime risk $\geq 20\%$

Intervention (N=10) (Day 0):

Bexarotene 1% gel at maximum tolerated dose from Part A Dose Escalation Group for 4 weeks.

Start Treatment (Day 1)

Start application of bexarotene gel to one unaffected breast

Phone Call (Day 8)

Assess adverse events and review Gel Diary

Study Visits (Day 15 and Day 28 (End of Study))

Assess for AEs & review gel diary. Labs to assess safety (CBC, LFTs, Lipid Profile, Thyroid Function Tests, Calcium) on Day 15 and 28 visits. Serum bexarotene collected on Day 28 visit. Mandatory breast biopsy at Day 28 visit.

Primary Endpoint: Safety and Toxicity

Secondary Endpoints: Serum and Tissue Bexarotene level, calcium, lipid and thyroid function biomarkers

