 - If a pregnancy is discovered after Day 0, instruct the participant to stop applying the gel, take participant off-study, complete the Off-Study CRF, follow the pregnancy to term and complete the Outcome of Pregnancy CRF.
- d) Research blood sample for serum bexarotene level.
- e) Participants need to have had any breast imaging with a normal/benign (bi-rads 1 or 2) result within 180 days of Day 0 and no further routine breast imaging planned during the course of the study (4 weeks). Exception: if the mammogram result was a bi-rads 0 and the imaging work-up (ultrasound and/or MRI) result comes back normal/benign (bi-rads 1 or 2) before treatment initiation, then participant is eligible.
- f) Participants must be instructed to apply the last dose of their study medication on the last day of the study (Day 28).
- g) Dermatology evaluation within 72 hours of study visit if participant experiences a grade 3 skin event or continues to have a persistent grade 2 skin event despite dose modification.
- h) The core biopsy at Day 28 is optional for dose escalation cohort participants. The biopsy is mandatory for participants in the dose expansion cohort at Day 28. If the participant is on aspirin, non-steroidal anti-inflammatory drugs or Vitamin E, she will be instructed to discontinue these 7 days prior to the end of treatment biopsy.
- i) See Appendix D “Alcohol and Tobacco Use Assessment Questionnaires – Baseline”.
- j) See Appendix E “Alcohol and Tobacco Use Assessment Questionnaires – Follow Up”.

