8. CRITERIA FOR EVALUATION AND ENDPOINT DEFINITION

8.1 Primary Endpoint: Toxicity and Safety

The primary objective of this study is to determine the safety and toxicity of topical 1% bexarotene gel application to the breasts of healthy women at high risk for breast cancer for duration of 4 weeks. Women with ADH, ALH, LCIS, breast cancer survivors (DCIS or invasive) \geq 5 years from their diagnosis, BRCA 1/2 mutation carriers, and women with elevated risk for breast cancer \geq 1.7% in 5 years or lifetime risk \geq 20% will be recruited. Three dose levels are considered (10mg every other day, 10mg daily, and 20mg daily). Dose Limiting Toxicity (DLT) is defined as a grade 2 skin adverse event that persists for at least 6 days or any grade 3 or greater adverse event possibly, probably, or definitely related to the study drug. In addition, a DLT will be a grade 2 skin adverse event that recurs and persists for at least 3 days. A conservative modification of the standard “3+3” design will be applied. The first cohort of 3 participants will be treated at the first dose level (10mg every other day). New cohorts of participants will not be treated until toxicity has been fully evaluated for all current participants for 4 weeks. We will add another 4 participants when only 1 or less participants experience DLT in 6 treated participants. We will only escalate dose to the next higher level when 20% or less of total participants experience a DLT. At any dose level, the algorithm is as follows:

- (1) If 0 or 1 out of 3 participants experience DLTs (\leq 1/3), an additional cohort of 3 participants will be treated at the same dose level. If total number of participants experiencing DLT at that dose level is 1 or less out of 6 (\leq 1/6), we will enroll another 4 at the same dose level.
- (2) If at any time 2 or more participants experience DLTs in 3 or 6 (\geq 2/3 or \geq 2/6) or 3 or more experience DLT in 10 participants (\geq 3/10), then the dose escalation will stop, and the next lower dose will be considered as the maximum tolerated dose (MTD).
- (3) In 10 participants at each dose level, if we observe 2 or less DLTs, a cohort of 3 will be treated at the next higher level. If 3 or more in 10 participants experience DLT, we will stop accrual to that level and above, and claim the regimen as to be too toxic for that level or above.

MTD is defined the highest dose level with at most 2 participants with DLTs in 10 participants treated.

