
1. Complete the diary daily.
2. If you miss an application, do not take an extra application to “make up” for the missed application.

If your next dose is scheduled within the next 24 hours, it is best just to wait; if it is more than 24 hours until your next dose, apply the dose you missed and resume your normal dosing after that.
3. If you accidentally pump more than is needed for one breast, please discard this dose and try again to get correct dose. If you do discard pumped doses, please record this on your Gel Diary.
4. Do not discard the gel canister. Bring the canister and this diary to your next appointment.
5. Store the study gel at home at room temperature and avoid extreme heat or cold during transportation from the clinic to home.
6. If you experience any concerning side effects or changes in the texture of your skin (e.g., skin feels like sandpaper), call _____ (insert name of Study Coordinator or Study Nurse) at _____ (insert telephone number) or the study doctor, [name] at [contact] for guidance.

Bexarotene Gel Diary: Dose Expansion Group (Continued)

Please Bring this Sheet and Empty Canister to Your Next Visit

	Day	Date	R or L Breast, OR Did not apply	Initials	Did you experience any symptoms, if "Yes" list below List # of discarded pumps of gel here
Week 1 Apply 1 pump to the breast every other day	1		 R  L  Did not apply		
	2		 R  L  Did not apply		
	3		 R  L  Did not apply		
	4		 R  L  Did not apply		
	5		 R  L  Did not apply		
	6		 R  L  Did not apply		
	7		 R  L  Did not apply		
Week 2 Apply 1 pump to the breast every other day	8		 R  L  Did not apply		
	9		 R  L  Did not apply		
	10		 R  L  Did not apply		
	11		 R  L  Did not apply		

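### The skin rules act at 3 and 6 days of Grade 2 toxicity, but scheduled skin checks are 7 to 13 days apart and no participant instruction is tied to 3 days

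*Combined protocol and SAP*

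**What the plan says.** **The triggers.** Section 5.5 holds drug for related Grade 2 skin toxicity "that persists for 3 days, drug will be held for 3 days". Table 1 then gives a restart step if the skin has settled to Grade 1 or less. Section 8.1, repeated in 13.4, gives the endpoint: "Dose Limiting Toxicity (DLT) is defined as a grade 2 skin adverse event that persists for at least 6 days". It adds that "a DLT will be a grade 2 skin adverse event that recurs and persists for at least 3 days".

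**The scheduled contacts.** Section 7.1 has a Day 8 call and visits on Days 15 and 28, each with a window of 2 days either way. Appendix G scripts the skin questions for those three contacts only. Section 5.5 says that "at Day 22 blood specimen will be added for monitoring", but only where Grade 1 hypertriglyceridemia has been noted, and it is not a skin check.

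**The unscheduled routes.**
- The expansion diary (Appendix C) says: "If you experience any concerning side effects or changes in the texture of your skin (e.g., skin feels like sandpaper), call" the study team. It is completed daily and has a symptom column without grade or area.
- Section 8.1 has women shown what a quarter of the treated area looks like. They are told to outline red areas and pass on any change, with no time limit.
- Appendix B asks for next-day notice of ulcers, blisters or open skin.
- Appendix B also offers the supplied moisturizer for redness.

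**Retrospective capture.** Section 7.4 has an adverse event assessment at Day 28 with the diary reviewed and collected. Section 13.7 records grade, attribution, onset and resolution dates for all toxicities.

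**The concern.** A rule that acts on the third day of an event works only if someone on the study team knows by then. On the schedule alone they often will not, and least often in the second half of treatment.

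This bears on what the primary endpoint measures. The hold trigger plus the hold length is 3 + 3 = 6 days, which is also the DLT threshold. Where the hold is applied, a first-episode DLT is an event that did not settle while drug was withheld. Where the hold is missed, the same label describes an event under continued dosing. The count at the MTD would then mix the two.

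The instructions can also steer a participant away from calling. Table 3 grades dry skin with erythema or itch as Grade 2. Appendix B meets redness with a moisturizer. A woman with dry, red skin could follow her sheet correctly, moisturize and not call.

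**Working it through.** **The plan's own figure.** The plan gives no figure for surveillance. The nearest is the early-stopping probability in 8.1 and 13.4: 15%, 51% and 82% at true DLT rates of 0.10, 0.20 and 0.30. With boundaries 2/3, 2/6, 3/10, 4/11–14, 5/15–19 and 6/20, an exact binomial recursion gives 14.97%, 51.3% and 82.3%. The figure reproduces, and this point does not challenge it.

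**Step 1: gaps (Section 7.1).**
- Day 1 to Day 8: 8 − 1 = 7 days.
- Day 8 to Day 15: 15 − 8 = 7 days.
- Day 15 to Day 28: 28 − 15 = 13 days, or 13/28 = 46% of treatment.
- Last gap with windows: shortest (28 − 2) − (15 + 2) = 9 days, longest (28 + 2) − (15 − 2) = 17 days.

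Each nominal gap is longer than 3 days and longer than 6.

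**Step 2: which onset days are covered by a scheduled contact.** Let Grade 2 toxicity start on day d and persist. The hold trigger is met by d + 3 and the DLT threshold by d + 6. A contact helps if it falls on d + 3, d + 4 or d + 5.
- Day 8 covers onsets on Days 3–5, and Day 15 covers Days 10–12: 6 of 14 onset days in Days 1–14.
- Day 28 covers onsets on Days 23–25: 3 of 14 in Days 15–28.
- Section 7.1 puts the last dose on Day 28, so those three are found when no treatment remains. On nominal days, 0 of 14 late onsets are found in time for a hold to act.
- Other day-counting conventions and the visit windows give 5–8 of 14 for Days 1–14 and 3–5 of 14 for Days 15–28.
- A persisting event with onset after the Day 15 visit and up to Day 22 reaches 6 days by Day 28 with no scheduled contact in between.

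**Step 3: a worked case.** Grade 2 starts on Day 16, at 10 mg every other day from Day 1 (odd days).
- Hold trigger: Grade 2 on Days 16, 17 and 18, so the hold covers Days 19–21.
- Hold missed: doses on Days 19, 21, 23, 25 and 27, which is five.
- Hold applied and skin settles: under Table 1, one dose for Days 22–24 (Day 22), then Days 25 and 27, which is three.
- Net difference: 5 − 3 = 2 doses.
- If the skin does not settle during the hold, Days 16–21 make 6 days and the event is a DLT even with perfect contact.

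A Day 28 dose is left out of both counts.

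**Step 4: effect of a Day 22 contact.** It adds onsets on Days 17–19. Late coverage rises from 3 to 6 of 14, and coverage before the last-dose visit from 0 to 3 of 14. The longest gap falls from 13 to 7 days, which still exceeds both triggers.

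**Step 5: effect on stopping.** Section 3 reports 0 DLTs in the 10 escalation women at this dose. From 0/10, the remaining pooled boundaries are crossed during the expansion with probability 0.1%, 2.0% and 10.0% at true rates of 0.10, 0.20 and 0.30. Under the pooled rule, misclassified events would mainly change the reported count and would seldom stop the trial.

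**The case against.** The strongest reply is that the plan does not leave participants unobserved. They are taught to judge area, outline redness and report changes. They have two call triggers in the diary and a next-day rule for broken skin. Consent pages are not available here and may say more. The lowest dose level had no DLT in 10 women. A Day 22 call would only bring the second half to the 7-day spacing already accepted in the first.

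Much of this stands. It rules out four stronger readings that a reader might infer.
- *Late events go unrecorded.* They need not. The diary is dated and daily, and Day 28 review with onset and resolution dates allows capture. The weakness is retrospective grading from an ungraded column.
- *Late events will run to DLT.* They may. Any of the reporting routes could bring a call in time.
- *A missed hold means five extra doses.* Table 1 resumes dosing after the hold, so the net in the worked case is about two.
- *One such DLT among the first three women ends the trial.* Under Section 3, 1/3 = 33% meets its 30% rule. Under 8.1 and 13.4, the pooled count would be 1/13 against a boundary of 4. That conflict between stopping rules is a separate matter and is not caused by the contact schedule.

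What the reply does not answer is that no route mentions 3 days. Nor does 0/10 validate the schedule: Section 3 describes the same schedule for both groups, and the one-sided 95% upper bound is 1 − 0.05^(1/10) = 26%.

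**Conclusion.** The point holds as a mismatch between the skin rules and the means of detecting their triggers. It is widest after Day 15 but not confined to that period, since 8 of 14 onset days before Day 15 are also uncovered by a scheduled contact. A late Grade 2 event may miss its hold and reach the DLT definition, or have its grade and duration settled at Day 28 from diary notes and recall.

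The size is a 13-day gap (9 to 17) against triggers of 3 and 6 days, and about two net extra doses in the Day 16 case. That case assumes the skin would have settled during the hold. The coverage counts assume persistent events, nominal visit days and no unscheduled call, so they describe the schedule and do not estimate missed holds. The documents give no rate of late-onset Grade 2 events and show no sign of harm so far. This is an inexpensive improvement worth making. It does not invalidate the design.

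**What to change.** Reconcile the participant instructions and contact schedule with the 3-day rule already in Section 5.5, leaving every dose, hold, restart and DLT rule as it is.

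1. Main change: add one line to the Dose Expansion Group diary and to Appendix B telling the participant to call the study team when redness, rash, itch or pain of the treated skin is present on three consecutive days. Place it beside the moisturizer advice so that the two are read together. It works on every treatment day, including before Day 15.
2. Supporting option: consider a Day 22 call for all expansion participants, using the Day 8 script, with matching entries in 7.1, 7.3 and Appendix G. It would not be enough alone, because 7-day gaps would remain.

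The cost is an amended sheet and, if the option is taken, about 10 calls by existing staff. The one downside is that surveillance becomes slightly closer than in the 10 escalation women with whom DLTs are pooled under 8.1 and 13.4. The report should say so.
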